3.2.4 Other Endpoints

1. Change from parent-study and OA-07-study baseline in medial joint space width (mJSW) as documented by radiograph of the target knee at Visit 2E (Week 24)
2. Change from parent-study and OA-07-study baseline OA pain, function, and stiffness as a composite outcome measure as assessed by WOMAC Total score and Stiffness at Visit 2E (Week 24) and Visit 3E (Week 48)
3. Change from parent-study and OA-07-study baseline in mJSW, pain NRS, WOMAC Pain, and WOMAC Function at Visit 6E (Week 100) compared to test values (carry forward and progression assumptions) derived from the change from baseline estimates from the Placebo group at Visit 3E (Week 48)
4. Change from parent-study baseline health-related quality of life (HRQOL) as assessed by the 36-Item Short Form Health Survey (SF-36) at Visit 3E (Week 48)
5. Percentage of subjects who consider themselves to be in Patient Acceptable Symptom State (PASS) at Visit 3E (Week 48)

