4. STUDY DESIGN

4.1 DESCRIPTION OF THE STUDY DESIGN

This study will be a multicenter study in subjects previously enrolled in study SM04690-OA-11. The first 48 weeks will be single-blind and placebo-controlled while the remainder of the study will be open-label and uncontrolled. The study is planned to continue at least until commercial availability of LOR. Based on previous studies, up to approximately 500 subjects will be enrolled, but there is no set cap on enrollment. Subjects must enroll no later than 6 weeks following completion of study SM04690-OA-11. Clinic visits will be scheduled at Visit 1E (Day 1), Visit 2E (Week 24), Visit 3E (Week 48), Visit 4E (Week 52 phone visit), Visit 5E (Week 74), and every 26 weeks thereafter until the Termination Visit. Refer to [Figure 1](#) for an overview of study design and endpoints.

At the first visit in this study (Visit 1E), all subjects will complete PASS and pain NRS assessments and then receive a blinded study injection into their target knee (the same target knee injected in the parent study), with subjects receiving the same treatment (either 0.07 mg LOR or placebo) as they received in the parent study. Subjects will have clinic visits for pain and function assessments, collection of AEs, and knee radiographs. At Visit 3E, subjects will have plasma samples collected for assessment of biomarkers of bone and cartilage turnover, and all subjects, regardless of previous treatment, will receive an injection of 0.07 mg LOR into their target knee. Subjects will receive injections of 0.07 mg LOR into their target knee every 52 weeks thereafter. Specific timing of protocol procedures is described in the Schedule of Events Table ([Section 7.3.4](#)).

Subjects are allowed to use non-steroidal anti-inflammatory drugs (NSAIDs) and/or acetaminophen for pain relief as needed. If a subject has a partial or total knee replacement of the target knee, the subject will be discontinued from the study.

Recording of signs and symptoms of study medication intolerability and AE reporting will start immediately following the parent-study EOS (End of Study) visit and continue at all subsequent

visits until the subject completes the Termination Visit. All AEs, whether volunteered, elicited, or noted during examination, will be recorded throughout the study.

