10.4.3 ANALYSIS OF EFFICACY ENDPOINT(S)

Change over time through Visit 3E in mJSW, pain NRS, WOMAC Pain, WOMAC Function, and WOMAC Total will be characterized using mixed-effects models for repeated measures (MMRM). The models will estimate change from parent-study baseline with treatment, visit, treatment \times visit interaction, and parent-study baseline value as covariates. Unadjusted 95% confidence intervals and *P* values will be reported. The potential confounding effect of change in NSAID/acetaminophen usage on the treatment effect will be considered for sensitivity analysis.

ANCOVA will be used to analyze the change in SF-36 domain scores and summary component scores through Visit 3E. Change will be assessed from parent-study baseline between the active and placebo treatment groups. The models will be adjusted for parent-study baseline. Unadjusted 95% confidence intervals and *P* values will be reported.

PASS will be analyzed using logistic regression. Logistic regression will also be used to compare the proportion of Outcome Measures in Rheumatology Clinical Trials (OMERACT)-Osteoarthritis Research Society International (OARSI) responders and “strict” responders ([Pham et al. 2003](#)) between treatment groups through Visit 3E, as well as proportion of subjects achieving a 20%, 50%, and 70% improvement.

Maintenance of LOR’s effects on pain and function of the target knee will be characterized by summarizing likelihood of response in pain NRS, WOMAC Pain, and WOMAC Function in the current study for those subjects that had a response in the parent study. Response will be characterized as a 20%, 50%, and 70% improvement.

After all subjects have received LOR at Visit 3E, all further efficacy analyses will be descriptive in nature.

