4. OVERALL STUDY DESIGN AND PLAN

This study was a multicenter study in subjects previously enrolled in study SM04690-OA-11. The first 48 weeks were single-blind and placebo-controlled while the remainder of the study was open-label and uncontrolled. At Visit 1E (Day 1) subjects received a single dose of LOR or placebo injected into the target knee joint as treated in the SM04690-OA-11 study. On and after Visit 3E (Week 48) subjects only received LOR injections.

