9.6.5 Open Label Portion of Study (Placebo Subjects Cross Over to LOR)

On and after Visit 3E (Week 48) all subjects only received LOR injections.

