9.6.5.2 Analysis

For each group of interest described in Section 9.6.5.1, we will estimate an mJSW baseline-adjusted ANCOVA at Visit 6E (Week 100) and test the difference against two test values:

- Carry-forward (i.e., no change) assumption test value will use the mJSW baseline-adjusted ANCOVA estimate at Visit 3E (Week 48) from the Placebo group.
- Progression (i.e., worsening) assumption test value will use the mJSW baseline-adjusted ANCOVA estimate at Visit 3E (Week 48) from the Placebo group extrapolated to a presumption of continued Placebo use.

Analysis will be performed using the parent and OA-07 study baselines.

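### SAP 3.2.4(3) lists Week 100 pain and function for comparison with Week 48 placebo values; the rest of the SAP defines that comparison for mJSW only, and for open-label self-reports it cannot isolate a LOR effect

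*SAP*

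**What the plan says.** Among the Other Endpoints, SAP 3.2.4 item 3 lists "Change from parent-study and OA-07-study baseline in mJSW, pain NRS, WOMAC Pain, and WOMAC Function at Visit 6E (Week 100) compared to test values". The test values, named as carry forward and progression, come from the placebo group's change-from-baseline estimates at Visit 3E.

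The method is in SAP 9.6.5.2: for Placebo-LOR, LOR-LOR and the pooled group, "we will estimate an mJSW baseline-adjusted ANCOVA at Visit 6E (Week 100) and test the difference against two test values". Carry-forward takes the Week 48 placebo estimate unchanged. The second value is described as follows: "Progression (i.e., worsening) assumption test value will use the mJSW baseline-adjusted ANCOVA estimate at Visit 3E (Week 48) from the Placebo group extrapolated" on the presumption that placebo had continued. No formula is given for the extrapolation.

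On design, SAP section 4 states: "The first 48 weeks were single-blind and placebo-controlled while the remainder of the study was open-label and uncontrolled". SAP 9.6.5 adds: "On and after Visit 3E (Week 48) all subjects only received LOR injections". Protocol 10.4.3 says that once all subjects have received LOR at Visit 3E, "all further efficacy analyses will be descriptive in nature". SAP section 13 records a departure from that rule, gives a study team decision as the reason, and refers the reader to a section 9.4.4 that the SAP does not contain.

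**The concern.** The endpoint list and the method sections disagree about which outcomes enter the Week 100 comparison. An analyst must either leave three listed endpoints unanalysed or carry a rule written for mJSW over to pain and function.

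The second course would cause harm. mJSW is documented by an independent radiologist at the central imaging vendor (protocol 7.1.1). Pain NRS and WOMAC are completed by the subject, who at Week 100 knows that LOR was injected at Visit 3E. The reference scores come from subjects who did not know what they had received. A difference in LOR's favour could therefore be reported as long-term symptom benefit when the design cannot attribute it to the drug.

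**Working it through.** The documents state no test value, alpha level, power or sample size calculation for this endpoint, so there is no figure of the plan's own to reproduce.

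**1. Which outcomes are covered at Week 100**

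| Place in the SAP | Outcomes compared with placebo test values |
|---|---|
| 3.2.4, item 3 | mJSW, pain NRS, WOMAC Pain, WOMAC Function |
| 9.1, other hypothesis 6 | mJSW |
| 9.2, other hypothesis 6 | mJSW |
| 9.6.5.2 | mJSW |
| Appendix 2, Week 100 rows (three groups) | mJSW |

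The concordance analysis in 9.6.4 uses pain and function response at Week 100, but relates it to mJSW within each group, not to placebo test values.

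**2. What differs between the two sides of the comparison**

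- *Knowledge of treatment.* Week 48 is single-blind; Week 100 is open-label.
- *Time.* The two assessments are 100 − 48 = 52 weeks apart, with no concurrent control at the later one.
- *Who is measured.* The groups in 9.6.5.1 require the Visit 3E injection. Subjects can leave for lack of efficacy or target-knee replacement (protocol 5.6.1), so those scored at Week 100 need not resemble the placebo group at Week 48.

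None of these is sampling error, so no choice of standard error removes them.

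**3. Illustration of the expectation effect on pain NRS**

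Assumptions, none of them in the documents: SD of change 2.4; 150 or 200 subjects in a sequence; no LOR effect; open-label shift s = 0.5 points; fixed carry-forward value; two-sided 5% test. SAP 7.1.2 gives a two-sided alternative but no alpha.

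P(falsely favourable) = Φ(s√n/SD − 1.96)

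- n = 150: SE = 2.4/√150 = 0.196; 0.5/0.196 = 2.55; Φ(0.59) = 0.72
- n = 200: SE = 2.4/√200 = 0.170; 0.5/0.170 = 2.95; Φ(0.99) = 0.84

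Over a wider range (SD 2.0 to 2.5, n 100 to 250):

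- shift 0.25: 17% to 51%
- shift 0.5: 52% to 98%
- shift 1.0: 98% to 100%

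With no shift, the rate is the nominal 2.5%.

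Allowing for sampling error in an independent reference of equal size (SE × √2) lowers the 0.5-point result to 44% to 55%. That model could apply at most to LOR-LOR, because Placebo-LOR subjects are placebo reference subjects measured again later.

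**4. What the progression rule would do if carried over to pain**

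Assume proportional scaling of the change from baseline. Parent baseline to Visit 3E is about 56 + 48 = 104 weeks, and to Visit 6E about 56 + 100 = 156 weeks, taking Visit 1E at the parent-study Week 56 visit (protocol 7.3.1). The multiplier is 156/104 = 1.50. From the OA-07 baseline it is 100/48 = 2.08.

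- Placebo pain change −2 (improvement): the progression value becomes −3.0 or −4.17, a larger improvement under a worsening label.
- Placebo pain change +1 (worsening): it becomes +1.5 or +2.08, and the label is right.
- With placebo at −2, no LOR effect and a shift of 0.5, the Week 100 mean is −2.5. That is 0.5 better than carry-forward (−2.0) and 0.5 worse than progression from parent baseline (−3.0).

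**The case against.** The strongest reply is that the SAP specifies no pain or function test at Week 100. A reader might infer from 3.2.4(3) that P values for these outcomes are planned; no method section says so. On that view the defect is one endpoint line without a matching analysis, in the lowest tier of endpoints. This stands as to what is specified. It does not make the line harmless, since anyone who carried out the listed endpoint would produce the comparison described above.

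A reader might also infer that the progression value would turn worsening into improvement. The documents do not support that as a general statement. It needs proportional extrapolation and a placebo group that has improved, and the documents give neither an extrapolation rule nor placebo results. Extrapolating the Week 24 to Week 48 trend, or a placebo group that worsened from the OA-07 baseline, need not produce it. Where it did occur, the benchmark would be harder for LOR to beat, whereas expectation favours LOR.

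Nor are the percentages predictions. The study injection is the last procedure at injection visits (protocol 7.3.4, footnote b), so Week 100 scores are taken about 52 weeks after the first open-label injection, and nothing in the documents shows that a 0.5-point expectation effect would last that long. That objection to the size holds. It leaves the structural problem in place, because time and retention remain confounded with LOR even if expectation has faded.

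Finally, SAP 7.1 already provides descriptive summaries at each visit, and section 13 openly discloses the departure from the protocol. Both are true; neither reconciles 3.2.4(3) with 9.6.5.2.

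**Conclusion.** The inconsistency within the SAP is certain from the text. It is also certain, from the design alone, that a Week 100 symptom comparison against Week 48 placebo values cannot identify a LOR effect.

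The size of the resulting bias is unknown. The 72% to 84% figure shows only how a modest shift could matter under the assumed SD, group size, fixed test value and absence of a LOR effect. The reversal of the progression value is a conditional side point.

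The main analyses in SAP 9.4 and 9.5 end at Week 48 and are not touched, so this is a change that should be made rather than a threat to the trial's main result.

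**What to change.** Delete pain NRS, WOMAC Pain and WOMAC Function from SAP 3.2.4(3). That leaves mJSW, in line with 9.1(6), 9.2(6), 9.6.5.2 and Appendix 2.

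Report the three outcomes at Visits 5E and 6E descriptively by sequence (Placebo-LOR, LOR-LOR), labelled open-label and uncontrolled. This returns them to the protocol's descriptive rule. Both instruments are already collected at those visits (protocol 7.3.2). Confidence intervals of 95% for the means are an optional addition; protocol 10.4.3 does not mention them for this period. The same edit can correct the section 9.4.4 cross-reference in SAP section 13, since the analysis is in 9.6.5.

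The cost is a one-line change to the endpoint list and labels on the summaries. The sponsor gives up a listed symptom comparison at Week 100.

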4. OVERALL STUDY DESIGN AND PLAN

This study was a multicenter study in subjects previously enrolled in study SM04690-OA-11. The first 48 weeks were single-blind and placebo-controlled while the remainder of the study was open-label and uncontrolled. At Visit 1E (Day 1) subjects received a single dose of LOR or placebo injected into the target knee joint as treated in the SM04690-OA-11 study. On and after Visit 3E (Week 48) subjects only received LOR injections.

4.1 Changes to Overall Study Design and Plan

The sponsor elected to administratively terminate this study. All active subjects were requested to continue the study until they completed Visit 6E (Week 100); subjects injected at this visit were followed-up via phone call 10 days (+/-3 days) for safety data collection. Subjects that had already completed their Visit 6E (Week 100) were asked to schedule a termination visit as soon as possible. All procedures for the termination visit should be performed; however, as provided in the protocol, an additional X-ray was not required if a subject had an X-ray taken within the 12 weeks prior to their termination visit.

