5.6 PARTICIPANT WITHDRAWAL OR TERMINATION

5.6.1 REASONS FOR WITHDRAWAL OR TERMINATION

Best efforts will be made to encourage subjects to attend all study visits. Subjects will be informed that they are free to withdraw from the study at any time and for any reason. A discontinuation from the study will occur when a subject who signed informed consent and was dosed ceases participation in this study, regardless of circumstances.

Subjects can be discontinued from the study for one of the following reasons:

- AE
- Total or partial knee replacement of the target knee
- Lost to follow-up after a minimum of 3 attempts have been made to contact the subject, including sending a registered letter
- Withdrawal by subject for reason other than lack of efficacy
- Subject noncompliance
- Physician decision for reason other than lack of efficacy
- Study terminated by Sponsor
- Site terminated by Sponsor

- Request by regulatory authority
- Lack of efficacy
- Pregnancy
- Death
- Other

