5.6.2 HANDLING OF PARTICIPANT WITHDRAWALS OR TERMINATION

All Termination Visit procedures and assessments should be performed on subjects who are withdrawn or who voluntarily withdraw, including subjects who withdraw due to partial or total knee replacement. The date the subject is withdrawn from the study and the reason for the discontinuation should be recorded on the electronic case report form (eCRF). The Investigator or designee must complete all applicable eCRFs for subjects who discontinue from the study.

Replacement of subjects who withdraw or discontinue is not allowed.

Total or Partial Knee Replacement Follow-Up

A subject who has had total or partial knee replacement of the target knee should be discontinued from the study. In addition to Termination Visit procedures, sites should make every attempt to follow up with these subjects approximately 6 months after the total or partial knee replacement surgery is completed to assess outcomes of the surgery.

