8.3 TIME PERIOD AND FREQUENCY FOR EVENT ASSESSMENT AND FOLLOW-UP

The reporting period for AEs starts immediately following the parent-study EOS visit and ends after the final study visit.

AEs will be followed until the subject's last visit or resolution, whichever comes first. For subjects who discontinue from the study within 30 days of their last study injection, AEs that are ongoing at the subject's last visit will be followed for 30 days after administration of the last dose or until resolution, whichever comes first. Resolution is defined as the return to baseline status or stabilization of the condition. SAEs and selected AEs identified by the Investigator or the Sponsor to warrant further follow-up that are ongoing at a subject's last visit will be followed until resolution.

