10.1 Adverse Events

Data regarding AEs will be collected in this study. As this is an extension trial, AE collection will continue from the parent study, ongoing AEs at the end of the parent study will continue to be monitored, and new AEs that occur during this study will be recorded. Changes to ongoing AEs that occur after the parent-study EOS visit will not be recorded in the parent study. AEs will be assessed through the Termination Visit. AEs will be presented in summary tables depicting the number and percent of unique subjects experiencing each AE and the number of AEs by the following analysis periods: (1) AEs that started prior to a Second OA-07 Injection (end of the single-blind, placebo-controlled period of the study; including all AEs for subjects who only received the First OA-07 Injection to End of Study, EOS), (2) on or after Second OA-07 Injection to prior to Third OA-07 Injection (including all AEs for subjects who received the Second OA-07 Injection to EOS), and (3) on or after Third OA-07 Injection to EOS. The following summaries will be provided:

- All AEs and all SAEs by severity and relationship to study product
- AEs by highest degree of seriousness, severity, and relationship to study drug
- AEs by MedDRA system organ class and preferred term
- SAEs sorted by preferred term incidence
- AEs with incidence of greater than 2% in the active treatment group sorted by preferred term incidence
- Target-knee-related AEs and SAEs sorted by preferred term incidence
- AEs leading to study withdrawal, discontinuation of study drug, or death
- SAEs in subjects diagnosed with COVID-19

If an AE start or end date is incomplete, it will be imputed in a way that assumes maximum exposure time (see table in [Appendix 3 – Partial Date Imputation](#)). Separate subject-level listings will be provided for all AEs and all SAEs.

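### AE incidence after the third OA-07 injection pools subjects scheduled for a phone call at 7 to 13 days with subjects followed to a Termination Visit, so the crude percentages are biased downward

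*SAP*

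**What the plan says.** SAP 4.1 reports an administrative termination by the sponsor and describes two routes out of the study.

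- **Active subjects** were asked to continue to Visit 6E, and "subjects injected at this visit were followed-up via phone call 10 days (+/-3 days) for safety data collection".
- **Subjects already past that visit:** "Subjects that had already completed their Visit 6E (Week 100) were asked to schedule a termination visit as soon as possible". The next sentence adds that "All procedures for the termination visit should be performed". It does not say whether this also covers the phone-call group.

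SAP 10.1 says that "AEs will be assessed through the Termination Visit". Its third AE analysis period runs from the third OA-07 injection to end of study. It is summarised as numbers and percentages of subjects, and the listed tables include preferred terms above 2% incidence. End of study is not defined for a subject whose last scheduled contact is the call.

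The protocol has its own rules.

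- Section 5.6.1 lists "Study terminated by Sponsor" among the reasons for discontinuation.
- Section 5.6.2 states: "All Termination Visit procedures and assessments should be performed on subjects who are withdrawn or who voluntarily withdraw". Section 7.3.3 lists those procedures, which include physical and knee examination, vital signs and laboratory tests.
- Section 8.3 sets a conditional rule, also given in 7.1.1. "For subjects who discontinue from the study within 30 days of their last study injection", AEs still open at the final visit "will be followed for 30 days after administration of the last dose or until resolution, whichever comes first". SAEs, and AEs selected by the investigator or sponsor, are followed to resolution.

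SAP 13 records changes to the analysis and does not mention AE follow-up.

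**The concern.** The third period is the only AE summary covering a third OA-07 injection. A percentage of subjects with an AE is interpretable when the subjects were observed for similar lengths of time and in similar ways. Here one group has a single scheduled telephone contact within two weeks. The other has follow-up to a clinic visit with examinations, vital signs and laboratory tests, which can themselves give rise to AEs. Pooling them adds the first group to the denominator in full while giving it little time to contribute to the numerator.

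A reader of the period 3 tables could take a low percentage, or an event that stays under the 2% cut, as a property of the third injection when part of it reflects short observation. SAP 10.1 compounds this by naming the Termination Visit as the end of AE assessment for everyone, when SAP 4.1 does not clearly give that visit to the phone-call group.

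**Working it through.** The plan states no figure on this point, so there is none to reproduce. The check is a comparison of texts plus day arithmetic.

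**1. Which injection.** OA-07 injections are at Visits 1E, 3E and 6E (Protocol 7.3.4), so the Visit 6E injection is the third and opens period 3.

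**2. Scheduled observation on the phone route.** 10 − 3 = 7 days to 10 + 3 = 13 days.

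**3. What the protocol schedule would have given.** The next visit after Week 100 is Visit 7E at Week 126: (126 − 100) × 7 = 182 days, nominal. The call falls at 7/182 = 3.8% to 13/182 = 7.1% of that interval. After the second injection (Visit 3E, Week 48) the safety call was due at (52 − 48) × 7 = 28 days, or 21 to 35 days with the ± 7 day window if Visit 3E was on time. Periods 2 and 3 therefore also differ in early contact.

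**4. Observation per 100 subjects injected** (100 × days / 365.25):

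| Observed to | Days | Person-years |
|---|---|---|
| Call, earliest | 7 | 1.92 |
| Call, nominal | 10 | 2.74 |
| Call, latest | 13 | 3.56 |
| Day 30 | 30 | 8.21 |
| Visit 7E, nominal | 182 | 49.83 |

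**5. Direction of the bias.** Let p be the share of period 3 subjects on the phone route, d their observation time, and T the mean observation time of the others. With a low, constant event rate, crude incidence relative to observing everyone for T is about 1 − p(1 − d/T). This is below 1 whenever p > 0 and d < T. Neither p nor T is documented. If T is assumed to be 182 days, the ratio runs from 1 at p = 0 to 0.04 (d = 7) or 0.07 (d = 13) at p = 1. These are bounds under an assumption, not an estimate. If AEs cluster in the first days after injection, the bias is smaller.

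**6. Kind of ascertainment.** Injection is the last procedure at an injection visit (Protocol 7.3.4, footnote b), so the Visit 6E laboratory tests, vital signs and knee examination precede the third injection. Clinically significant findings from these assessments are to be reported as AEs (Protocol 7.1.1, 7.2.1). The Termination Visit offers a set after the injection; the call cannot. The general physical examination is scheduled only at Visit 3E and the Termination Visit.

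**7. The 30-day rule.** The call is 30 − 13 = 17 to 30 − 7 = 23 days before day 30; 7/30 = 23% and 13/30 = 43%. These figures locate the call. They do not measure a loss, because the rule concerns AEs already open at the final visit and sets no search for new ones to day 30.

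**The case against.** A reader might infer that the SAP stops AE follow-up at the call, that AE outcomes are cut short, and that 57% to 77% of the protocol's 30-day window is lost. The documents do not support this. SAP 4.1 says the call was for collecting safety data. It does not say that follow-up ended there or that any protocol rule was waived. An AE found open at the call could still be followed to day 30, and an SAE to resolution. SAP 10.1 plans no table of AE outcome or duration, and an AE open at the call is already counted.

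A reader might also infer that phone-call subjects certainly had no examination or laboratory test after the third injection. That is not established either, because the sentence requiring all termination procedures can be read as covering both groups. The ordinary schedule also has no laboratory tests or vital signs at Visit 7E; the next would be at Visit 8E, 52 weeks after Visit 6E.

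Three further points are fair. SAP 4.1 discloses the change openly. SAP 3.2.3 limits the AE endpoint to the time before the second OA-07 injection. Period 3 is uncontrolled, and no formal safety tests are planned.

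These points limit the consequences but do not remove the pooling. The protocol's AE endpoint (3.2.1) covers the whole study, SAP 10.1 does tabulate period 3, and unequal observation for new AEs affects those percentages whatever happened to AEs already open at the call.

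**Conclusion.** The concern holds as a defect in how period 3 is reported and defined. Run as written, SAP 10.1 pools 7 to 13 days of scheduled observation by telephone with follow-up to a clinic Termination Visit, and the resulting crude incidence, including the 2% table, is biased downward. The size cannot be computed: the number of subjects on each route and the time from third injection to Termination Visit are not stated.

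The conclusion rests on three assumptions: that some subjects are on each route; that Termination Visit subjects were on average observed for longer than 13 days, although a subject only just past Visit 6E may not have been; and that AEs are not confined to the first days after injection.

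Whether AE follow-up stopped at the call is not documented, so no fraction of the 30-day window should be reported as lost. Separately, SAP 4.1 and 10.1 and Protocol 5.6.2, 7.1.1, 7.3.3 and 8.3 do not together tell the reader which follow-up applied to the phone-call group. They must be reconciled.

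**What to change.** - **SAP 10.1, tables.** Report period 3 by follow-up route (phone call only versus Termination Visit). Give the number of subjects and the observation time for each, or exposure-adjusted rates. Apply the 2% table within route, or show it with its observation time. List AEs unresolved at last contact.
- **SAP 10.1, definition.** Define end of study for the phone-call group, and correct the statement that AEs are assessed through the Termination Visit if it does not apply to them.
- **SAP 4.1.** State whether the Termination Visit, and the protocol's follow-up of open AEs, SAEs and selected AEs, applied to subjects injected at Visit 6E. Reconcile 4.1 and 10.1 with Protocol 5.6.2, 7.1.1, 7.3.3 and 8.3, and record any departure. Which follow-up rule is clinically appropriate is for the sponsor to settle.

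The cost is a few sentences and one extra table, using injection and last-contact dates. The downside is smaller groups in period 3 and so less precise percentages. Visits already conducted cannot be changed, but the reporting can.
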